4.2.1.3 Rationale for Study Design

The pangenotypic preclinical profiles of MK-3682 and MK-8408, as well as the preliminary results from the three-drug, 8- and 12-week regimens of MK-3682/GZR/MK-8408 in GT1, GT2 and GT3 support the preliminary evaluation of the safety and efficacy of 12 weeks of MK-3682+MK-8408 in treatment-naïve or prior IFN-based treatment experienced, non-cirrhotic and compensated cirrhotic GT1-, GT2-, GT3-, GT4-, GT-5, and GT-6-infected

subjects. A treatment duration of 12-weeks for all genotypes using the MK-3682+MK-8408 combination in this study is supported by the equipotent or superior *in vitro* potency profiles of MK-3682 and MK-8408 (Table 2 and Table 3) compared to other compounds of the same classes, such as the approved NI/NS5A SOF/LDV or SOF/VEL, that have demonstrated high efficacy rates against GT1-6 after 12 weeks of treatment as two-drug IFN-free DAA regimens. RBV is not proposed to be evaluated in this study given the high efficacy rates observed with other two-drug all-oral DAA regimens without RBV, such as SOF/LDV and SOF/VEL, and the equipotent or superior *in vitro* potency profiles of MK-3682 and MK-8408 compared to these regimens.

Since this is an estimation study, no comparator or placebo is used. No statistical comparisons are planned for efficacy and safety data. The target number of GT1-, GT2-, GT3-, and GT4-infected subjects is specified in order to provide sufficient confidence of the estimated treatment response rate in these genotypes, since they are the most prevalent genotypes globally. Since subjects with genotypes 5 and 6 are uncommon outside of certain geographic areas, the study will enroll approximately a targeted number of subjects with the assumption that full enrollment of these genotypes may not be reached.

If a total of ≥ 3 out of the first 10 subjects in the per-protocol population of the 12 week arms experience virologic relapse by FW4, all subjects already enrolled and on treatment for that GT will have their treatment duration extended to 16 weeks. This treatment duration modification rule was chosen in order to stop a regimen that had a reasonable probability of being insufficiently effective (in this case because of insufficient duration), while not prematurely discontinuing a regimen that could be successful. This choice was based on the following calculations to estimate the probability of observing a given number of subjects with virologic failure rates assuming a range of true SVR rates. Assuming a protocol violation rate of 10%, the PP population will include approximately 9 subjects out of the first ten of each genotype. The probability of observing 3 or more subjects with virologic failure out of 9 subjects per arm is 53.7%, 39.9%, 26.2%, 14.1%, and 5.3% assuming the true SVR rates of 70, 75, 80, 85, and 90%, respectively. Detailed information on these calculations is in Section 8.7. This modification rule provides an approximately 40% probability of extending treatment duration of a given genotype in the study for a true SVR rate of 75% or less, but is unlikely to extend the treatment duration if the SVR rate is 90% or higher (which is the SVR rate expected from a competitive regimen).

Patients who fail the MK-3682+MK-8408 regimen will be followed long-term, as described in Sec. 7.1.5.6. No rescue medications are included in this trial because it is not clear which rescue regimen would be optimal for patients who fail MK-3682+MK-8408. Subjects who experience virologic failure will be considered for future therapy once data are available to guide selection of rescue regimens. The composition and duration of future retreatment will be informed not only by the efficacy and RAVs observed at baseline and at failure in this study, but also from results from ongoing Phase 2 studies of MK-3682B. The efficacy of MK-3682B in cirrhotic and non-cirrhotic patients at different durations in GT1-6 is being evaluated in Part B of MK-3682 PN011 and PN012. In addition, results from Part C of MK-3682 PN011 and PN012, in which subjects who failed 8-week regimens of MK-3682+ GZR + either MK-8408 or EBR, are being retreated with a regimen consisting of 16 weeks of MK-3682B plus RBV, may provide insights into the optimal treatment for these patients. MK-3682 PN021 is evaluating retreatment of GT1-infected patients who have previously failed

all-oral DAA regimens with regimens of 16 weeks of MK-3682B plus RBV or 24 weeks of MK-3682B without RBV. The role of RAVs in virologic failures in these studies will be analyzed and results from other retreatment studies using currently available therapies will be considered in evaluating the optimal retreatment regimen for potential subjects who fail treatment in this study.

Additional stopping rules are described in Section 5.11.

4.2.2 Rationale for Dose Selection/Regimen/Modification

The regimen selected for administration in this trial is 450mg of MK-3682 + 60mg of MK-8408 administered concomitantly once daily as separate medications.

4.2.2.1 Dose Selection for MK-3682

The 450mg dose of MK-3682 was chosen for this study based on the dose-response analysis generated by monotherapy data from MK-3682 PN001. This analysis suggests that the 450mg dose of the tablet formulation is on the plateau of the dose-response curve and would provide a greater margin to loss of efficacy than would the 300mg of the tablet formulation, while still maintaining margins to preclinical safety exposures. Although the 300mg and 450mg MK-3682 dose arms had comparable efficacy in GT3-infected subjects in PN012 Part A (SVR₁₂ of 39/42 (93%) and 39/44 (89%), respectively), a slightly higher efficacy was observed in GT2-infected subjects in MK-3682 PN011 Part A who were on the 450mg dose of MK-3682, with an SVR₁₂ rate of 77% (24/31) versus 70% (21/30) on the 300 mg dose. The highest efficacy in GT2-infected subjects was observed in the MK-3682 (450mg)/GZR/MK-8408 arm with an SVR₁₂ rate of 94% (15/16), supporting the selection of this regimen for this study. In addition, the 450mg dose of MK-3682 has demonstrated an acceptable safety profile in Part A of MK-3682B PN011 and PN012 when co-administered with GZR and MK-8408 or MK-8742.

4.2.2.2 Dose Selection for MK-8408

The 60mg dose of MK-8408 was chosen for the MK-3682B FDC regimen based on the available safety, tolerability, and pharmacokinetic data from the single and multiple dose and drug-interaction studies in healthy volunteers and the pharmacokinetic, pharmacodynamic (PD) and safety profiles of MK-8408 in HCV infected subjects. Preliminary pharmacodynamic data from PN003 are available for doses up to 120 mg in HCV GT3 subjects and demonstrate that following once daily fasted dosing of 10, 30, 60, and 120 mg MK-8408 for 5 days, the mean maximum reduction in HCV VL was -2.83, -3.03, -3.35 and -1.75 log₁₀ IU/mL, respectively. The anomalous fall in VL decline at 120 mg dose of MK-8408 was explained by sequencing of the HCV subjects' isolates that revealed that all 3 subjects in this panel had either baseline or treatment-emergent resistance-associated variant viruses. One subject had the resistant variants S62L/Y93H at baseline and following treatment; this subject had a maximal VL reduction of -0.34 log₁₀ IU/mL. One subject had no detectable RAVs at baseline but had both S62L and Y93H emerge during treatment; this subject had a -1.85log₁₀ IU/mL VL reduction. The third subject had A30K at baseline with emergence of Y93H/Y during treatment; this subject had a -3.06log₁₀ IU/mL VL reduction. These VL results demonstrate that 30 mg and 60mg of MK-8408 are associated with a substantial and rapid initial VL decline of GT3, but that MK-8408 may not exhibit full

efficacy against some GT3 RAVs in the setting of monotherapy administration. Following a single dose of 60mg MK-8408 once-daily \times 5 days the mean maximum reduction in HCV VL in GT1a subjects was $-3.86 \log_{10}$ IU/mL, and the mean maximum reduction in HCV VL in GT2b subjects was $-3.62 \log_{10}$ IU/mL. For detailed information, please refer to the MK-8408 IB.

The fit-for-purpose capsule formulation of MK-8408 demonstrates a moderate negative food effect, with a 50% decrease in C24hr when co-administered with a high fat meal. As such, in this study, subjects will be instructed to take study drugs on an empty stomach after an overnight fast, at least 1 hour before the morning meal. Study drugs should be taken with water, but without food. Drug-drug interaction studies with MK-3682 and MK-8408 (MK-3682 PN007 and MK-3682 PN008) demonstrated no clinically significant drug interactions, thus supporting the coadministration of these drugs without need for dose adjustment.

4.2.3 Rationale for Endpoints

4.2.3.1 Efficacy Endpoints

The primary measurement for efficacy in this study is the plasma HCV RNA level. Long-term suppression of HCV RNA, typically reported as SVR, has been associated with improved outcomes in subjects with chronic HCV infection as measured by biochemical and histological remission of liver disease. Most available data suggest that SVR following antiviral therapy reduces the risk of progression to cirrhosis and may prevent the development of severe liver complications as well as improve survival [43].

The primary evaluation of efficacy in this trial is based on SVR₁₂, the same endpoint used for all investigational and approved DAAs (e.g., simeprevir, SOF). Since a high degree of concordance has been observed between SVR₁₂ and SVR₂₄ [44], SVR₁₂ is now being used as the primary endpoint for registration of DAAs. A secondary evaluation of efficacy is based on SVR₂₄ (Sustained Virologic Response 24 weeks after the end of all study therapy), and for this study this will be a secondary endpoint [45].

4.2.3.1.1 Measurement of HCV RNA

HCV-RNA levels in plasma will be measured using the Roche COBAS[®] AmpliPrep/COBAS[®] TaqMan[®] HCV Test, v2.0 on blood samples drawn from each subject at various time points prior to, during, and after dosing, as indicated in the Study Flow Chart (Section 6.0). Samples are collected and processed as per instructions provided by the manufacturer.

Results from the sample collected at the screening visit are used to determine eligibility. Samples collected at other time points, after Day 1, are used for efficacy analyses and to identify subjects who meet virologic failure criteria.

The nomenclature detailed in [Table 7](#) will be used when describing HCV RNA levels:

Table 7 Nomenclature for Describing HCV RNA Levels

Abbreviation	Definition	HCV RNA Level
TND	Target not detected	HCV RNA not detected
TD(u)	Target detected but unquantifiable	HCV RNA < LLOQ
TD(q)	Target detected, quantifiable	HCV RNA \geq LLOQ

4.2.3.1.1.1 Definition of Efficacy Endpoints

Efficacy will be defined at different timepoints during the trial. Specific primary and secondary endpoints are:

- SVR₄ (Sustained Virologic Response 4 weeks after the end of all study therapy). The subject has HCV RNA < LLOQ 4 weeks after the end of all study therapy.
- SVR₈ (Sustained Virologic Response 8 weeks after the end of all study therapy). The subject has HCV RNA < LLOQ 8 weeks after the end of all study therapy.
- SVR₁₂ (Sustained Virologic Response 12 weeks after the end of all study therapy). The subject has HCV RNA < LLOQ 12 weeks after the end of all study therapy.
- SVR₂₄ (Sustained Virologic Response 24 weeks after the end of all study therapy). The subject has HCV RNA < LLOQ 24 weeks after the end of all study therapy.
- Virologic failure rate among subjects who do not discontinue study for non-treatment-related reasons at FW12.

4.2.3.1.1.2 Definition of Virologic Failure: Non-Response, Rebound, Virologic Breakthrough and Relapse

Lack of efficacy at different time points in the trial will be categorized as:

- Non-response:
Subject has HCV RNA detected at end of treatment without HCV RNA < LLOQ having been achieved while on treatment (note that breakthrough is captured below).
- Rebound:
Subject has a rebound defined as $>1 \log_{10}$ IU/mL increase in HCV RNA from nadir while on treatment and confirmed from a separate blood draw within 2 weeks.
- Virologic breakthrough:
Subject has a confirmed HCV RNA \geq LLOQ after being < LLOQ previously while on treatment. Confirmation is defined as an HCV RNA \geq LLOQ from a separate blood draw repeated within 2 weeks.

- Relapse:

Subject has a confirmed HCV RNA \geq LLOQ following end of all study therapy, after becoming undetectable (TND) at end of treatment. Confirmation is defined as an HCV RNA \geq LLOQ from a separate blood draw repeated within 2 weeks.

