5.12 Clinical Criteria for Trial Modification

5.12.1 Efficacy Criteria for Modification of Treatment Duration

- If a total of ≥ 3 out of the first 10 subjects in the PP population enrolled in a 12-week dosing duration arm experience virologic relapse by FW4, the treatment duration of any remaining subjects of that genotype in that arm will be extended to 16 weeks and no further subjects will be enrolled in that 12 week treatment arm.

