7.1.5.4 Discontinued Subjects Continuing to be Monitored in the Trial

Discontinuation during Treatment Period

Subjects who discontinue therapy in the trial prior to the last scheduled treatment visit should have an Early Discontinuation visit and then continue into follow-up visits.

At a minimum, the following information should be collected:

- The reason the subject discontinued
- The date of the last dose of study medications from the trial

- The date of the last assessment and/or contact. A follow-up contact (telephone or visit) will be arranged as appropriate
- (Serious) Adverse events

Final Assessments:

- Every effort should be made to ensure that all procedures and evaluations scheduled for the Early Discontinuation Visit are performed.
- Retrieve all study medications from the subject.

Discontinuation for Virologic Failure

Subjects who discontinue because they have met criteria for virologic failure (Section 4.2.3.1.1.2) while on study therapy should complete an Early Discontinuation Visit as outlined in the Trial Flow Chart (Section 6.0), and return to the study site for follow-up visits at 4, 8, 12, and 24 weeks following confirmation of virologic failure.

Subjects who meet the virologic failure criterion for relapse (HCV RNA \geq LLOQ following the end of all study therapy, after becoming undetectable [TND] at the end of treatment) will return to the study site for the remainder of their follow-up visits (e.g., 4, 8, 12, and 24 weeks) as outlined in the Trial Flow Chart (Section 6.0).

All subjects who take at least 1 dose of study drug, experience virologic failure, and complete FW24 should be offered long-term follow-up (see Section 7.1.5.6).

Discontinuation during Follow-Up Period(s)

Subjects who discontinue during the follow-up period (e.g. follow-up visits at 4 through 24 weeks after EOT) for reasons other than virologic failure should complete an Early Discontinuation Visit as outlined in the Trial Flow Chart. Subjects who discontinue from the long-term follow-up period (e.g. through 3 years after EOT) should complete an Unscheduled Visit as outlined in the Long-Term Follow up section of the Trial Flow Chart.

At a minimum, the following information should be collected:

- The reason the subject discontinued
- The date of the last assessment and/or contact. A follow-up contact (telephone or visit) will be arranged as appropriate
- SAEs (per reporting requirements outlined in Section 7.2)

Discontinuation of Long Term Follow-Up

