7.1.5.5 Post-Trial

At the completion of study therapy subjects will return to the study site for follow-up visits at 4, 8, 12, and 24 weeks after the last dose of study drug. Virtual visits by telephone will occur at follow-up weeks 16 and 20.

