1. Treatment-Related Discontinuation = Failure (TRD=F) approach: Subjects with treatment-related missing data (type #2 above) will be considered as failure; whereas the subjects who have the non-treatment-related missing value (type #3 above) and who do not have virologic failure during the observed study period will be excluded from the analysis for the time points following their study withdrawal. Note that subjects with documented virologic failure during the treatment or follow-up period, even if they withdrew prematurely due to reasons not related to study drug, are classified as failures.
2. Missing=Failure (M=F) approach: Subjects with any non-intermittent missing data (i.e., type #2 and #3 above) will be imputed as failures, regardless of the reason for study discontinuation.

In addition, a missing baseline/Day 1 HCV RNA result will be replaced with a screening result, if available.

Proportions of Subjects With Virologic Responses and Virologic Failures

For the primary efficacy analysis, the proportions of subjects achieving SVR₁₂ after 12 weeks of treatment in each treatment arm will be provided and 95% confidence intervals for these rates will be calculated using the Clopper-Pearson method [49]. The same method will be used to analyze all binary endpoints including SVR₂₄ after 12 weeks of treatment.

For all analyses conducted using the PP and mFAS populations, the missing data approach of TRD=F will be utilized. In addition, for all analyses in these two populations, a subject will be considered to have achieved a particular endpoint if the HCV RNA levels for the infection he/she had at baseline are < LLOQ. In other words, if a subject has HCV RNA levels \geq LLOQ at a particular time point, but those RNA levels correspond to an infection that is of a different genotype and/or subtype compared to the infection detected at baseline and the baseline infection has been cleared, then the subject is considered to have achieved response for the given endpoint.

Sensitivity analyses that use the FAS population will utilize the M=F missing data approach. Also, in the FAS analyses, only subjects with HCV RNA levels < LLOQ for any type of HCV infection at a given time point will be considered to have achieved the endpoint.

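### A subject with a quantifiable HCV RNA at FW4 or FW8 who is lost before the 2-week retest and before FW12 can leave the primary SVR12 analysis instead of counting as a failure

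*Combined protocol and SAP*

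**What the plan says.** **Relapse.** Section 4.2.3.1.1.2 requires a confirmed HCV RNA at or above LLOQ after target not detected at end of treatment, the confirming value coming "from a separate blood draw repeated within 2 weeks". Breakthrough has the same limit, and rebound must be "confirmed from a separate blood draw within 2 weeks". Nothing covers a retest that is late or absent.

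**A second wording.** Section 7.1.5.4 describes the relapse criterion as HCV RNA at or above LLOQ "following the end of all study therapy, after becoming undetectable [TND] at the end of treatment", with no mention of a second draw.

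**Visits.** Section 7.1.5.5 schedules "follow-up visits at 4, 8, 12, and 24 weeks after the last dose of study drug". The flow chart in Section 6.0 adds an unscheduled viral failure confirmation visit with HCV RNA, and gives the follow-up visits a window of -1 to +2 weeks.

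**SVR12.** The endpoint rests on one value: "The subject has HCV RNA < LLOQ 12 weeks after the end of all study therapy". Table 16 defines non-response in PP and mFAS as HCV RNA at or above LLOQ for the baseline infection, also without confirmation.

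**Missing data.** Section 8.6.1 places loss to follow-up among reasons unrelated to study drug and assumes missing at random. Under TRD=F, used for PP (primary) and mFAS, subjects with such missing data "who do not have virologic failure during the observed study period will be excluded from the analysis for the time points" after they withdraw. Early leavers with documented virologic failure stay in as failures, but *documented* is not defined. The FAS analysis uses Missing=Failure.

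**Decision rules.** Sections 5.11.3, 5.12.1 and 8.7 count how many of the first 10 PP subjects in an arm "experience virologic relapse by FW4" (5.11.3 also counts non-response, rebound and breakthrough).

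**The concern.** The 2-week limit does two jobs. It is a sensible instruction to sites about when to retest. As part of the endpoint definition, it also decides who is a virologic failure, and through TRD=F who stays in the primary denominator.

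The subject at issue has undetectable RNA at end of treatment, a quantifiable value at FW4 or FW8, and no further sample. The observed data point to failure. If the relapse definition in 4.2.3.1.1.2 is applied as written, though, no virologic failure has occurred, the missing FW12 value is classed as unrelated to treatment, and the subject is removed. Missing at random cannot justify this, because the removed subject is not exchangeable with those who remain: the last observed value already shows virus.

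The error always favours the regimen, and PP arms of about 22 or 45 are sensitive to one subject. Section 8.5.1 leaves final exclusions to a memo before database lock in an open-label trial, so the choice between the two relapse wordings could be made with results in view.

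**Working it through.** **1. Follow the subject through the rules.**

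| Step | Text | Result |
|---|---|---|
| FW4 or FW8 RNA at or above LLOQ, no retest | 4.2.3.1.1.2 | not confirmed, so not relapse |
| same value | 7.1.5.4 | relapse |
| lost to follow-up before FW12 | 8.6.1 | unrelated to drug |
| PP and mFAS, TRD=F | 8.6.1 | excluded if no virologic failure; failure if it is documented |
| FAS, M=F | 8.6.1 | failure |

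Whether this subject is in the primary denominator therefore depends on which wording of relapse the analyst uses.

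**2. Subjects who stay to FW12.** A subject with quantifiable FW4 and FW8 values, no retest within 2 weeks and an observed FW12 value is classified for SVR12 by that FW12 value. If FW12 is missing between two observed values, 8.6.1 imputes the worse of them. SVR12 is not inflated in either case. The late or missed retest can matter only for the FW12 virologic-failure endpoint and possibly the first-10 count.

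**3. Reproduce the plan's intervals.** Clopper-Pearson limits for x successes in n are the 2.5% quantile of Beta(x, n-x+1) and the 97.5% quantile of Beta(x+1, n-x). For 20/22 this gives 70.8% to 98.9%, and for 41/45 it gives 78.8% to 97.5%. Both agree with Table 19.

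**4. Remove k such subjects.** Successes stay at x; the denominator becomes n-k.

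| Table 19 case | k=0 | k=1 | k=2 |
|---|---|---|---|
| 20 successes, n=22 | 20/22 = 90.9% (70.8, 98.9) | 20/21 = 95.2% (76.2, 99.9) | 20/20 = 100% (83.2, 100) |
| 41 successes, n=45 | 41/45 = 91.1% (78.8, 97.5) | 41/44 = 93.2% (81.3, 98.6) | 41/43 = 95.3% (84.2, 99.4) |

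One subject adds 4.3 points in the smaller arm and 2.1 in the larger. The values of k are assumptions; the documents give no rate of relapse followed by loss.

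**5. The first-10 rule.** The binomial probability of 3 or more failures in 10 is 61.7% at true SVR 70%, as in Table 18. Suppose, purely for illustration, that every failure is a relapse by FW4 and that a share q = 20% of relapses is never confirmed. If those subjects stay in the 10 as non-failures, the failure rate is 0.30 × 0.80 = 0.24 and the probability is 44.4%. If they leave PP and the next PP subject takes their place, the rate is 0.24/(1 - 0.30 × 0.20) = 0.2553 and the probability is 49.0%. The answer depends on q and on the handling, and the documents fix neither.

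**The case against.** The strongest reply is that exclusion is only one reading. Section 7.1.5.4 gives relapse without confirmation, *documented* in 8.6.1 could cover a recorded value at or above LLOQ, and Section 8.5.1 removes administrative non-virologic failures from PP, which does not clearly describe a subject whose last value is quantifiable. The prespecified FAS analysis counts every such subject as a failure, so the bias would be visible in a study that tests no hypothesis. These points stand and limit the size of the problem. They do not remove it: the conflict is in the text, and FAS is supportive while PP is primary.

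A reader might go further and infer that anyone retested late escapes failure and inflates SVR12. The documents do not support that. Those who reach FW12 are judged on that value. A positive retest 15 to 28 days after FW4 falls within 2 weeks of an on-schedule FW8 draw and can be confirmed by it. The visit windows can also bring FW4 and FW8 within 2 weeks of each other.

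Nor does the gap between follow-up visits show a matching problem for breakthrough, because on-treatment visits from Week 2 are nominally 2 weeks apart. A reader might also want to quote a definite loss of sensitivity for the first-10 rule; step 5 of the working shows that any such figure is an assumption.

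**Conclusion.** The point holds in a narrow form. Read literally, the confirmation rule in 4.2.3.1.1.2 combined with TRD=F removes from the PP and mFAS SVR12 analyses a subject with a quantifiable FW4 or FW8 value who is lost before retest and before FW12 for a reason classed as unrelated. Each such subject raises primary SVR12 by about 2 points in an arm of 45 and about 4 in an arm of 22, for the Table 19 cases used above. The number affected is unknown and may be zero.

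The effect on the FW12 virologic-failure endpoint and on the first-10 rules cannot be estimated from the documents. The sample size figures are not in question; the Table 18 and 19 values used here reproduce. The firm defect is that two definitions of relapse coexist and the missing-data rule does not say which one makes a failure documented.

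**What to change.** For the efficacy analyses only, add to Section 8.6.1:

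- In PP and mFAS, a last available post-treatment HCV RNA at or above LLOQ, not shown to be reinfection and with no later sample, counts as failure for SVR12, SVR24 and the FW12 virologic-failure endpoint. The reinfection clause is needed because Table 16 counts reinfection after clearance of the baseline infection as response.
- For the FW12 virologic-failure endpoint, a next available value at or above LLOQ confirms relapse whatever the interval.

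Reconcile the relapse wording in 4.2.3.1.1.2 and 7.1.5.4, and have the sponsor state which definition the enrolment and duration rules in 5.11.3, 5.12.1 and 8.7 use. The breakthrough and rebound criteria should stay untouched by this change, because Table 10 uses them to stop treatment.

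**Cost.** A few sentences, with no new visits or samples. A rare transient value in a subject who is then lost would count as failure, so SVR could be slightly understated. Such values do occur: Section 4.1.2.2.2 reports one subject among 135 with GT2 whose HCV RNA was 279 at Week 12 of treatment and undetectable at FW4 and FW8. Where a later sample exists, the added rule for a last value does not apply.

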4.2.3.1.2 Viral Resistance Measurements

Resistance associated variants (RAVs) in the hepatitis C virus can lead to failure of therapy. This is one of the most important considerations when treating with a DAA. To better understand and document the potential for RAVs to impact treatment with MK-3682+MK-8408, blood samples for viral resistance assays are collected at Baseline (Day 1) to determine pre-existing RAVs to MK-3682 and MK-8408. Additional resistance testing on these samples may be performed. Blood samples for resistance testing are also collected during the follow-up period, as well as at the virologic failure confirmation visit (should this occur) for genotypic and investigational assays to assess emergence of resistance to MK-3682 and/or MK-8408 following treatment initiation. RAVs will be assessed for any subject who has detectable virus above 1000 IU/mL and has met a virologic failure criteria.

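### Relapse requires target not detected at end of treatment, so a confirmed post-treatment failure in a subject detected below LLOQ at that visit fits no failure category, and the plan conflicts on whether the FW12 failure rate counts it

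*Combined protocol and SAP*

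**What the plan says.** Table 7 (Section 4.2.3.1.1) has two categories below quantification: TND, and TD(u), described as "Target detected but unquantifiable". Section 4.2.3.1.1.2 then defines four kinds of virologic failure:

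- Non-response: RNA detected at end of treatment "without HCV RNA < LLOQ having been achieved while on treatment".
- Rebound: a confirmed rise of more than 1 log10, worded as an "increase in HCV RNA from nadir while on treatment".
- Breakthrough: confirmed RNA at or above the LLOQ "after being < LLOQ previously while on treatment".
- Relapse: confirmed RNA at or above the LLOQ after all therapy, "after becoming undetectable (TND) at end of treatment". Section 7.1.5.4 repeats the condition: "after becoming undetectable [TND] at the end of treatment".

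Other sections rely on these terms:

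- The duration rule (Sections 2.1, 4.2.1.3, 5.12.1 and 8.7) counts relapse by FW4 in the first 10 PP subjects.
- The enrollment-stop rule (Section 5.11.3) counts the four categories by FW4.
- Section 8.4.1.1 describes FW12 virologic failure as on-treatment failure or post-treatment relapse.
- Table 16 (Section 8.6.1) names that same endpoint in its mFAS row and sets non-response as RNA at or above the LLOQ for the baseline infection, with no condition on end-of-treatment status.
- Section 4.2.3.1.2 states: "RAVs will be assessed for any subject who has detectable virus above 1000 IU/mL and has met a virologic failure criteria".

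**The concern.** The SVR endpoints use the LLOQ with no condition on the end-of-treatment result, and exploratory endpoint 2 (Section 8.4.1.3) treats TD(u) and TND alike as below LLOQ at end of treatment. The relapse definition does not. The protocol therefore has an on-treatment responder whose later confirmed viremia makes the subject an SVR12 non-responder but has no name among the virologic failures.

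Three things are at stake. First, a secondary endpoint can take two values from the same data, depending on which section the programmer follows. Second, two rules that act on 3 events among about 10 subjects do not count an observed failure. Third, the commitment to assay resistance variants is tied to a met failure criterion, so it does not cover this subject.

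**Working it through.** **Step 1. Test one subject against each definition.** The subject is TD(u) at end of treatment and has confirmed RNA at or above the LLOQ in follow-up.

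| Category | Met? | Reason |
|---|---|---|
| Non-response | No | TD(u) is below LLOQ, so below LLOQ was reached on treatment |
| Rebound | No | On-treatment event; the rise is after treatment |
| Breakthrough | No, on the ordinary reading | Table 10 makes it a reason to stop treatment; a Section 6.0 footnote uses it as an example of failure during therapy |
| Relapse | No | Not TND at end of treatment |
| SVR12, SVR24 | Non-responder if RNA is at or above LLOQ at that visit | No end-of-treatment condition |

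**Step 2. FW12 failure rate.** Illustration with 45 analysed (the PP size in Section 8.9.1; the mFAS size is not stated, so 45 is an assumption). Suppose 4 subjects have confirmed RNA at or above LLOQ for the baseline infection and 1 of them was TD(u) at end of treatment. The subject is in the denominator either way. Clopper-Pearson 95% intervals:

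- Section 8.4.1.1 with Section 4.2.3.1.1.2: 3/45 = 6.7% (1.4 to 18.3).
- Table 16: 4/45 = 8.9% (2.5 to 21.2).

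One subject is worth 1/45 = 2.2 points, or 1/22 = 4.5 points if 22 are analysed in Arm 5 or 6.

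**Step 3. Reproduce Table 18.** The formula is P(X ≥ 3) for X binomial(n, p) with p = 1 − true SVR. For n = 9 and p = 0.25:

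1 − [0.75^9 + 9(0.25)(0.75^8) + 36(0.25²)(0.75^7)] = 1 − [0.0751 + 0.2253 + 0.3003] = 0.399.

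This matches the printed 39.9%, and all 12 cells reproduce. Table 18 thus treats every non-SVR subject as an event.

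**Step 4. Effect of the gap.** Let q be the share of failures that are TD(u) at end of treatment. The counted event probability becomes (1 − SVR)(1 − q). The documents give no q; the values below are assumptions.

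| True SVR, n | Printed (q = 0) | q = 5% | q = 10% | q = 20% |
|---|---|---|---|---|
| 75%, n=9 | 39.9% | 36.4% | 33.0% | 26.2% |
| 75%, n=10 | 47.4% | 43.7% | 39.8% | 32.2% |
| 90%, n=9 | 5.3% | 4.6% | 4.0% | 3.0% |

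At q = 20% and n = 9, p = 0.25 × 0.80 = 0.20, so the result equals the printed figure for a true SVR of 80%.

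**Step 5. What the documents say about q.** On the three-drug regimen, Section 4.1.2.2.2 reports all GT1 and all GT3 Part B subjects undetectable at end of treatment. In GT3, 283 − 276 = 7 subjects lacked SVR, so 0 of 7 would fall in the gap. The exact two-sided 95% upper limit for 0/7 is 1 − 0.025^(1/7) = 41%, so these data suggest a small q without excluding the range above. GT2 is reported only as below LLOQ (134/135), which does not separate TND from TD(u).

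**The case against.** A reader might infer that such a subject drops out of the failure rate and that the rate is biased downward. The documents do not establish that. Section 8.6.1 presents Table 16 as the criteria for the secondary endpoints, and its mFAS row would count the subject. The defect there is a conflict between two criteria, and the subject stays in the denominator under both.

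Other points on the other side:

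- The breakthrough sentence is loose. Its reference to being on treatment can attach to the earlier value alone, which would capture the subject. Table 10 and the Section 6.0 footnote argue against that reading, but it is possible.
- Relapse is not the only definition that uses detection; non-response does too.
- Table 18 is not the duration rule's own trigger probability. It counts all failures, while the rule counts relapse by FW4, so its figures are already upper bounds. One missed subject changes a decision only when the count would otherwise be exactly 3.
- No resistance sample is lost. Plasma is collected at FW4, FW8, FW12 and FW24; only the commitment to assay is affected.
- One might infer that TD(u) subjects are at special risk of relapse. The documents contain no data on this.
- This is an estimation study without formal hypotheses, and the earlier data suggest that the case may be rare.

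These points stand and limit the size and severity. They do not close the classification gap or remove the conflict between Section 8.4.1.1 and Table 16.

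**Conclusion.** The gap is real as written: on the ordinary reading, a TD(u)-at-end-of-treatment subject with later confirmed quantifiable RNA fits none of the four categories. Neither sentinel rule counts this subject, and the commitment to assay resistance variants does not cover the subject. SVR12 and SVR24 are unaffected. For FW12 virologic failure the plan contradicts itself, by 2.2 points per subject if 45 are analysed.

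The effect on the Table 18 figures (39.9% to between 36.4% and 26.2% at SVR 75%, n=9) rests entirely on an assumed q of 5% to 20%. The three-drug GT1 and GT3 data suggest that q may be lower; this trial uses a two-drug regimen, for which the documents give no end-of-treatment data. Should be fixed.

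**What to change.** - For efficacy classification, define relapse as confirmed HCV RNA at or above the LLOQ after the end of all study therapy in a subject whose end-of-treatment result was below the LLOQ, whether TND or TD(u). Use this in Sections 4.2.3.1.1.2, 7.1.5.4 and 8.4.1.1 and in Section 8.6.1 with Table 16, so that FW12 virologic failure has one meaning.
- Add a programmed check that every SVR12 non-responder with confirmed RNA at or above the LLOQ for the baseline infection falls in a virologic-failure category. List unconfirmed values separately: a single unconfirmed FW12 value fails SVR12 without meeting the relapse definition, even after the rewrite.
- State that the rules in Sections 2.1, 4.2.1.3, 5.11.3, 5.12.1 and 8.7 use this term, note that the wider definition can add to their counts, and reconcile those sections with it. Their thresholds stay as they are. This point takes no position on the clinical rules themselves.

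The cost is wording and one check. The reported failure rate may be slightly higher. Subjects may already have entered long-term follow-up, according to the Amendment 04 text, so some sentinel decisions may be past. The classification and resistance analyses can still be corrected, since Section 8.0 provides for documented changes before final database lock.
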